#### Intercurrent events:

- SDCR withdrawal from study treatment: treatment policy
- NSDCR withdrawal from study treatment: hypothetical
- Taking rescue therapy: composite (included in variable definition)
- Treatment interruption due to infection: treatment policy

Summary measure: The difference in the proportion of responders at Week 24

An estimate of the treatment effect will be computed using a Cochran-Mantel-Haenszel test adjusting for the randomization stratification factors (background therapy, autoantibody type, and region). Data following a NSDCR withdrawal from study treatment and any missing data will be imputed using multiple imputation as in the primary estimand.

Two endpoints require different considerations:

- The proportion of patients with at least one gMG related exacerbation
- The proportion of patients receiving rescue therapy between baseline and Week 24

In the first case, it is not possible to start a rescue therapy before observing a gMG related exacerbation. In the second, the event of interest is starting a rescue therapy. Therefore, starting a rescue therapy is not considered an intercurrent event for these endpoints and consequently is not included in the estimand definition.

Supplementary estimands will be detailed in the SAP and will include using a composite approach for the intercurrent event of SDCR withdrawal from study treatment.

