4.1 GENERAL CONSIDERATION

In addition to specific analyses and presentations that are detailed in the following sections, study results will be presented by treatment arm (with total when appropriate) and summarized according to the nature of the variables.

For continuous variables, using descriptive statistics, including the number of participants contributing to summary statistics, mean, standard deviation, median, and range as appropriate.

For categorical variables, using the frequency and proportion of participants falling into each category, grouped by treatment arm (and total). The percentages given in these tables will be rounded and therefore may not always sum to 100%. If a missing category is not presented in the data display, only participants with non-missing values for the parameter being assessed will be included in the percentage calculation.

All efficacy analyses will be performed on the mITT (or subpopulations of the mITT) unless otherwise specified. If additional subpopulations are specified (i.e. AChR+ or AChR-), then the mITT restricted to those subpopulations will be analyzed. The mITT ensures that each participant is able to contribute a minimal meaningful amount of information to evaluate the treatment effect of satralizumab. The ITT and mITT exclude adolescents joining the study after the last adult participant is randomized. Adolescent participants not part of the mITT will be analyzed separately.

The primary efficacy analysis will be performed on the AChR+ participants. Participants will be analyzed according to the treatment assigned at randomization by the IxRS.

All safety analyses will be performed in the safety-evaluable population, unless otherwise specified. Participants will be analyzed according to the first treatment they received after randomization.

The baseline value will be defined as the last available value recorded prior to the initiation of study treatment, unless otherwise specified.

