4.2.3 Missing Data and Imputation

Obviously, the optimal strategy for dealing with missing data is to make every effort to obtain complete data during the conduct of the study. The Sponsor will work diligently and use a variety of methods to minimize the percentage of missing data in this trial. Nevertheless, there is likely to be a small percentage of missing data. In this context, approaches to handle missing data for the primary and secondary analysis are described in this section.

If a participant discontinues treatment the Sponsor will ensure all planned assessments are continued whenever possible to avoid unnecessary missingness.

The following missing data and imputation procedure applies to relevant baseline covariates (Stratification factors [auto-antibody type, background therapy and region]) and all longitudinal efficacy scores (MG-ADL, QMG, Myasthenia Gravis Composite [MGC], Myasthenia Gravis Quality of Life [MG-QoL] and Quality of Life in Neurological Disorders [Neuro-QoL]) including baseline.

In the following the resolution of different missingness types are described and will be addressed in the order listed.

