4.2.3.4 Imputation Due to Intercurrent Events

In the following we describe missingness and data imputation due to IECs. A detailed statistical justification for this imputation strategy can be found in Wolbers M et al. (2021).

- 1. For each participant the time of the first ICE is determined using the ICE data set. For each efficacy score a data set is created where all subsequent data to the first ICE is removed. If a participant has multiple ICEs between which normal dosing of study drug is attained all the data are nevertheless removed in a first step, i.e., data that would be dealt under treatment policy is still removed in this step. This ensures that the imputation model is fitted on data that is completely unaffected by ICEs.
- 2. A mixed model repeated measures (MMRM) model is fitted as an imputation model to address all the missingness due to ICEs. The MMRM is modeling change from baseline of the efficacy score (separate MMRMs will be fitted for each score) and has the following covariates: treatment group, visit, treatment group x visit, baseline stratification factors (background therapy, auto-antibody type [where this applies], region), baseline efficacy score and baseline efficacy score x visit. ("x" refers to complete interactions). The MMRM will use an unstructured covariance overall, in case of convergence issues the covariance structure will be simplified to compound symmetry. The resulting model will serve as a model for all imputations of longitudinal data in the next step.

3. The MMRM model implies a multivariate normal imputation distribution conditional on baseline covariates and conditional on observed longitudinal data that is not affected by an ICE. The implied conditional mean of this normal distribution is used to impute missing data. Participants with an ICE but subsequent data available which falls under treatment policy will use the observed data and will not be imputed. Participants on the satralizumab arm with missing data due to an ICE in category SDCR will be imputed using the imputation model and their treatment group covariate will be artificially set to placebo (copy reference imputation), this way their data are imputed as if they had not had a benefit from the treatment after the ICE. This imputation procedure will result in a complete data set for each efficacy score. All the efficacy analyses will be conducted on the completed data sets.

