4.2.3.5 Analysis and Inference of the Primary Endpoint

The treatment effect on the primary endpoint is estimated using an analysis of covariance (ANCOVA) with response variable change in MG-ADL from baseline to Week 24 adjusting for treatment group and the same covariates as for the imputation model.

The primary treatment effect estimate is the regression coefficient of the treatment group.

The estimate of variance coming from the ANCOVA will underestimate the true variance as it ignores the variance due to the imputation. To correct the underestimation of the variance the jackknife is applied to all previous steps (2-3) of the imputation modeling, that is an imputation model is fit on each data set with one participant removed. The p-value of the treatment effect is derived through the Wald test.

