AChR = acetylcholine receptor; AChR+ = AChR-antibody seropositive (participants/population); gMG = generalized Myasthenia Gravis; LRP4 = low-density lipoprotein receptor-related protein 4; MG-ADL = Myasthenia Gravis Activities of Daily Living; ; MGC = Myasthenia Gravis Composite; MG-QoL = Myasthenia Gravis Quality of Life; MuSK = muscle-specific kinase; NSDCR = not study drug or condition related; OP = overall population; QMG = Quantitative Myasthenia Gravis score; QoL = quality of life; SDCR = study drug or condition related; Exacerbation = increase of non-ocular MG-ADL item by at least two points from baseline or achieving non-ocular item value of 3 when baseline was below 3.

4.3.2 Secondary Endpoints Under the Primary (Continuous) Estimand Framework

Secondary endpoints falling under the primary estimand framework (Table 6) will be analyzed the same way as the primary endpoint. The ANCOVA model will be analyzed by adjusting for the baseline value of the corresponding score, i.e., QMG change from baseline to 24 weeks will be adjusted for baseline QMG (instead of baseline MG-ADL).

The estimands for the secondary endpoints will be derived on the imputed data set of the primary estimand if the corresponding endpoint is solely based on the raw score.

4.3.3 Secondary Endpoints Under the Responder Estimand

To analyze secondary endpoints under the responder estimand framework (Table 6) each participant will have to be labelled as a responder or non-responder. This is done using the complete data set from the Imputation procedure and by applying the definition of the secondary endpoints. For a rationale on those responder definitions refer to the Study Protocol sections on MG-ADL, QMG and MGC responder definitions, which employ minimum clinically important difference derived in the relevant clinical literature. According to ICE specification of the responder estimand, participants that received rescue therapy will be imputed as non-responders (composite strategy) irrespective of the actual score in the completed data set.

A Cochran-Mantel-Haenszel test over the treatment groups stratifying for baseline stratification factors is the treatment effect estimator for the responder estimand. The estimate is the difference in proportion at Week 24.

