4.3.4 Secondary Endpoints Under the Duration Estimand

The duration estimand is only relevant for the analysis of the number of consecutive visits a participant shows an MG-ADL reduction of at least 2 points from baseline. Based on the completed data set, the first time a participant shows a 2-point or more reduction from baseline, the duration is measured until Week 24 or until the visit when MG-ADL=is no longer reduced by 2 points from baseline MG-ADL. The duration is the difference in weeks between the two visits defining the start and end (or Week 24) of reduction from baseline. If the participant shows a reduction for only one visit, the count is set to 1 week. If the participant required rescue therapy, the count is stopped prior to the visit at which the participant received rescue therapy (composite).

The count variable (the number in weeks by consecutive visits) will be modeled using an ANCOVA adjusting for the same covariates as the imputation model and baseline MG-ADL. The treatment effect estimator is the regression coefficient of the treatment group. The estimate is the difference in the mean duration of meaningful improvement at Week 24.

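### The three point-reduction responder comparisons are not adjusted for the baseline score, unlike the primary, continuous secondary and duration analyses; the possible cost is a modest loss of precision on supportive endpoints

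*SAP*

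**What the plan says.** **Responder comparison.** SAP 4.3.3 states: "A Cochran-Mantel-Haenszel test over the treatment groups stratifying for baseline stratification factors is the treatment effect estimator for the responder estimand". It then names the difference in proportions at Week 24 as the estimate. Protocol 6.4.5 agrees: "Cochran-Mantel-Haenszel test adjusting for the randomization stratification factors (background therapy, autoantibody type, and region". SAP 4.2.3 lists the same three factors. Anyone who receives rescue therapy counts as a non-responder whatever the score (SAP 4.3.1.1 and 4.3.3).

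**Neighbouring analyses.**
- Primary (SAP 4.2.3.5): an ANCOVA "adjusting for treatment group and the same covariates as for the imputation model". Those covariates include "baseline efficacy score and baseline efficacy score x visit" (SAP 4.2.3.4).
- Continuous secondary endpoints (SAP 4.3.2): "The ANCOVA model will be analyzed by adjusting for the baseline value of the corresponding score".
- Duration of a 2-point MG-ADL improvement (SAP 4.3.4): "modeled using an ANCOVA adjusting for the same covariates as the imputation model and baseline MG-ADL".

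**Availability and status.** The baseline score is already defined: "The baseline value will be defined as the last available value recorded prior to the initiation of study treatment, unless otherwise specified" (SAP 4.1). SAP Table 6 rates the three point-reduction endpoints as supportive in the AChR+ and overall populations and as exploratory in the AChR- population. None of them is in the hierarchy of SAP 4.3.7.

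**The concern.** A fixed drop of 2 or 3 points may be easier to reach from a high score than from a low one. At the entry minimum of 5 on MG-ADL, a 2-point drop is 40% of the score; at 15 it is 13%. For QMG, Protocol 3.4.7.2 itself reports a different important-change threshold below and above a baseline of 16. If baseline predicts response, leaving it out of the comparison gives wider intervals than the same data allow.

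The contrast is sharpest for MG-ADL. Duration and response use the same 2-point threshold on the same score, yet the SAP adjusts only duration for baseline, and it gives no reason. In the AChR+ population antibody type is constant, so the stratified test works with background therapy and region alone.

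At stake is the width of the intervals for three clinically readable supportive endpoints. No confirmatory claim depends on them.

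**Working it through.** **1. The plan's own responder figure.** SAP 2.2 assumes 50% response on placebo and 75% on satralizumab, and states about 80% power. With d = 0.25, pooled proportion 0.625 and n per arm:

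power = Φ{ [d − 1.96·√(2·0.625·0.375/n)] / √[(0.5·0.5 + 0.75·0.25)/n] }

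- n = 80: (0.25 − 0.1500)/0.0740 = 1.352, power 0.912.
- n = 72 (80 less 10% withdrawal): (0.25 − 0.1582)/0.0780 = 1.178, power 0.881.

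Continuity correction or Fisher's exact test gives 0.84 to 0.88. The stated 80% is therefore not reproduced, but it errs on the cautious side: the unadjusted comparison already has more power than claimed at these rates.

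**2. Approximate effect of adjusting.** Let R be the within-arm correlation of baseline score with responder status. Adjustment multiplies the variance by about 1 − R². R is not in the documents, so a range is shown, at 80 per arm and 50% v 75%:

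| R (assumed) | Unadjusted/adjusted variance, 1/(1 − R²) | Power after adjustment |
|---|---|---|
| 0 | 1.00 | 0.912 |
| 0.2 | 1.04 | 0.922 |
| 0.3 | 1.10 | 0.935 |
| 0.4 | 1.19 | 0.952 |

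**3. Simulation of the MG-ADL endpoint as the SAP defines it.**
- From the documents: 80 per arm, changes of −2.3 and −4.3, SD 3.97, score range 0 to 24, a 2-point responder threshold, rescue in 10% (satralizumab) and 20% (placebo), and rescued participants set to non-response.
- Assumed: baseline mean 9, SD 3, minimum 5; four strata; the baseline-to-change correlation.
- Compared: the Mantel-Haenszel weighted risk difference, and a logistic model with treatment, strata and baseline score standardised to a marginal risk difference.

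Variance without adjustment divided by variance with adjustment:

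| Baseline-to-change correlation | Rescue independent of baseline | Rescue likelier at high baseline (assumed log-odds 0.5 per SD) |
|---|---|---|
| 0 | 1.00 | 1.00 |
| −0.3 | 1.02 | 1.01 |
| −0.45 | 1.09 | 1.04 |
| −0.6 | 1.16 | 1.06 |

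Repeat runs move these ratios by up to about 0.03. Without rescue the simulated response rates are about 58% and 76%. The rescue rule takes them to roughly 0.58 × 0.80 = 46% and 0.76 × 0.90 = 68%, against the SAP's 50% and 75%.

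**4. In practical terms.**
- Interval width scales with the square root: √1.02 = 1.01, √1.09 = 1.04, √1.16 = 1.08. Intervals are 1% to 8% wider.
- Sample-size equivalent, 1 − 1/ratio: 2%, 8% and 14%. In the second column it is 1%, 4% and 6%.

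**5. Validity.** In a separate simulation at 50% v 75%, both estimators were centred on the 25-point difference. With no effect, Cochran-Mantel-Haenszel rejected in 5.1% of runs and the adjusted test in 5.7% (Monte Carlo standard error 0.4 points).

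**The case against.** The strongest reply is that Cochran-Mantel-Haenszel is valid, simple and pre-specified, the endpoints are not confirmatory, and power at the stated rates already exceeds 80%. All of that stands, and it is why this is a minor point. Chance baseline imbalance is also already covered by the interval.

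The gain is conditional too. If baseline does not predict response, there is none. Most participants enter with MG-ADL of at least 5 and so have room for a 2-point drop. The rescue rule weakens the link further, because it makes some high-baseline participants non-responders regardless of score. Leaving rescue out gives ratios of about 1.03, 1.11 and 1.22, but those do not describe the endpoint that the SAP defines.

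Some stronger readings are tempting and are not supported:
- **The analysis ignores baseline.** It does not. Response is a reduction from baseline, and the imputation model contains the baseline score. What is missing is adjustment of the treatment comparison.
- **Every continuous analysis adjusts for baseline.** This holds for the primary, continuous secondary and SAP duration analyses. The SAP names no covariates for EQ-5D-5L (4.4.2.2) or the sustained-efficacy model (4.4.1), and the protocol's duration ANCOVA (6.4.7) lists only stratification factors.
- **The stratified test cannot deliver the stated summary measure.** The SAP does name the difference in proportions, and a Mantel-Haenszel weighted difference is its natural companion. Only the weights and the interval method are left unstated.

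**Conclusion.** The point holds as one of efficiency. The MG-ADL, QMG and MGC point-reduction comparisons leave out a collected covariate that the closest analyses include, without a stated reason. For MG-ADL the unadjusted variance is between 1.00 and about 1.16 times the adjusted one if rescue is unrelated to baseline, and at most about 1.06 times if rescue is likelier at high baseline. These figures rest on assumed correlations from 0 to −0.6, an assumed baseline distribution and the plan's rescue rates. No figure is offered for QMG or MGC. A reader might infer bias, an inflated error rate or a threat to the trial's main conclusion; nothing in the documents or the calculations supports any of these.

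**What to change.** In SAP 4.3.3, for the MG-ADL (at least 2 points), QMG (at least 3) and MGC (at least 3) responder endpoints in the AChR+ and overall populations:
- Fit a logistic regression on treatment, the stratification factors and the baseline value of the same score.
- Standardise it to a marginal difference in proportions with a 95% CI, so that the summary measure is unchanged.
- Pre-specify the variance method with a small-sample correction, for example the jackknife already used for the primary analysis. The 5.7% v 5.1% null rejection is the reason to state it.
- Keep Cochran-Mantel-Haenszel as the supportive test, and say which weights and interval method go with its difference in proportions.
- Keep Cochran-Mantel-Haenszel as the analysis for minimal symptom expression, for rescue and for the AChR- population. In simulation, adjustment did not reliably help minimal symptom expression (ratios 1.05, 1.02 and 0.82). The AChR- group has at most 25 participants, and at 12 per arm the logistic model came close to separation in about 5% to 8% of runs.

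The cost is SAP wording, settled before unblinding; no new data are needed. The downside is a model-based estimate in place of a simple stratified one.

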4.3.4 Secondary Endpoints Under the Duration Estimand

The duration estimand is only relevant for the analysis of the number of consecutive visits a participant shows an MG-ADL reduction of at least 2 points from baseline. Based on the completed data set, the first time a participant shows a 2-point or more reduction from baseline, the duration is measured until Week 24 or until the visit when MG-ADL=is no longer reduced by 2 points from baseline MG-ADL. The duration is the difference in weeks between the two visits defining the start and end (or Week 24) of reduction from baseline. If the participant shows a reduction for only one visit, the count is set to 1 week. If the participant required rescue therapy, the count is stopped prior to the visit at which the participant received rescue therapy (composite).

The count variable (the number in weeks by consecutive visits) will be modeled using an ANCOVA adjusting for the same covariates as the imputation model and baseline MG-ADL. The treatment effect estimator is the regression coefficient of the treatment group. The estimate is the difference in the mean duration of meaningful improvement at Week 24.

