## 6.4.7 Duration Estimand and Estimator

The elements of the duration estimand are defined below using the AChR + population as an example:

- Population: Patients with AChR+ gMG as defined by the study inclusion and exclusion criteria
- Secondary efficacy variable: Number of consecutive visits when a patient achieved a ≥ 2-point reduction from baseline in MG-ADL, without receiving rescue therapy
- Treatment: satralizumab 120 mg (for patients with body weight ≤ 100 kg) or 180 mg (for patients with body weight > 100 kg) versus matching placebo, administered for 24 weeks, in combination with stable background therapy

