1.1 OBJECTIVES AND ENDPOINTS

This study will evaluate the efficacy, safety, PK, and pharmacodynamics (PD) of satralizumab compared with placebo in participants with gMG on stable background therapy. In addition, the study will assess the long-term safety and efficacy of satralizumab during the open-label extension (OLE) period.

The study has the following objectives and corresponding endpoints (Table 1).

Table 1 Objectives and Corresponding Endpoints

Primary Efficacy Objective	Corresponding Endpoint
To evaluate the efficacy of satralizumab versus placebo on function in daily life in the AChR+ population	Mean change from baseline in total MG-ADL score at Week 24
Secondary Efficacy Objectives	Corresponding Endpoints
To evaluate the efficacy of satralizumab versus placebo on function in daily life in the OP	Mean change from baseline in total MG-ADL score at Week 24
To evaluate the efficacy of satralizumab versus placebo in the AChR+ and OP on:	
 Function in daily life 	Percentage of participants with a ≥2-point reduction from baseline in total MG-ADL score at Week 24 ^a
 QMG, QoL, and Fatigue 	Mean change from baseline in QMG score, MG-QOL 15r total score and Neuro-QoL Fatigue Subscale total score at Week 24
	Percentage of participants with a ≥3-point reduction from baseline in QMG score at Week 24 ^a

 Table 1
 Objectives and Corresponding Endpoints

	- Clinical status	•	Mean change from baseline in total MGC score at Week 24
		•	Percentage of participants with a ≥3-point reduction from baseline in total MGC score at Week 24 ^a
	 Disease severity 	•	Proportion of participants:
		•	Who have achieved minimal symptom expression (total MG-ADL score of 0 or 1) at Week 24 a
		•	With at least one gMG-related exacerbation between baseline and Week 24
		•	Receiving rescue therapy between baseline and Week 24
•	To evaluate the durability of the efficacy of satralizumab versus placebo in the AChR+ population and the OP	•	Duration (average number of consecutive months) of meaningful improvement, defined as ≥2-point reduction from baseline in total MG-ADL score ^a
	Exploratory Efficacy Objectives		Corresponding Endpoints
•	To evaluate the efficacy of satralizumab versus placebo in the AChR+ and OP on		
	- Time-to-event	•	Time to disease improvement as measured by:
			 ≥2-point reduction in total MG-ADL score or
			 ≥3-point reduction in QMG score or
			 ≥3-point reduction in total MGC score or
			 MG-ADL score of 0 or 1 (minimal symptom expression)

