Mean change from baseline in	AChR+	confirmatory		
Neuro-QoL Fatigue Subscale total score at Week 24	OP	supportive		
total soore at Wook 24	LRP4 & MuSK	exploratory		
	AChR+, OP	supportive		

 Table 6
 Secondary Endpoints and Corresponding Estimand and Relevance

Secondary Endpoint	Population	Relevance	Estimand Type (Generic)
Percentage of participants with a ≥2-point (and more) reduction from baseline in total MG-ADL score at Week 24	LRP4 & MuSK	exploratory	reduction from baseline in Score at Week 24 between participants treated with satralizumab vs placebo, in combination with stable background therapy, as though participants with treatment discontinuation due to NSDCR continued treatment and as though participants with missing data after SDCR, treatment interruption due to infection continued with placebo as though participants receiving rescue therapy were not showing a reduction from baseline.
Percentage of participants with a	AChR+, OP	supportive	
≥3-point (and more) reduction from baseline in QMG score at Week 24	LRP4 & MuSK	exploratory	
Percentage of participants with a	AChR+, OP	supportive	
≥3-point (and more) reduction from baseline in total MGC score at Week 24	LRP4 & MuSK	exploratory	
Proportion of participants who	AChR+, OP	supportive	
have achieved minimal symptom expression (total MG-ADL score of 0 or 1) at Week 24	LRP4 & MuSK	exploratory	
Proportion of participants with at	AChR+, OP	supportive	
least one gMG related exacerbation between baseline and Week 24	LRP4 & MuSK	exploratory	

Duration (# consecutive	AChR+, OP		Duration Estimand: The difference in the mean duration of meaningful improvement at
visits) that participants show at least 2 point reduction from baseline MG-ADL	LRP4 & MuSK	exploratory	Week 24 in population between participants treated with satralizumab vs placebo, in combination with stable background therapy, as though participants with treatment discontinuation due to NSDCR continued treatment and as though participants with missing data after SDCR, treatment interruption due to infection continued with placebo as though
WIG-ADL			participants receiving rescue therapy were not showing a further reduction from baseline.

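### Read literally, SAP 4.3.4 ends a lapsed run of response at the first visit without response, so losing response at Week 24 scores the same as keeping it, which does not match the plan's own count of consecutive responding visits

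*SAP*

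**What the plan says.** SAP 4.3.4 starts the clock at "the first time a participant shows a 2-point or more reduction from baseline". It then states that "the duration is measured until Week 24 or until the visit when MG-ADL=is no longer reduced by 2 points from baseline MG-ADL", and that "The duration is the difference in weeks between the two visits defining the start and end (or Week 24) of reduction from baseline". Two special rules follow:

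- One responding visit: "If the participant shows a reduction for only one visit, the count is set to 1 week".
- Rescue: "the count is stopped prior to the visit at which the participant received rescue therapy".

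The result is analysed in weeks by ANCOVA, and the estimate is a difference in mean duration.

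The variable is described differently elsewhere:

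- Protocol 6.4.7 defines it as "Number of consecutive visits when a patient achieved a" reduction of 2 points or more, without rescue.
- SAP Table 6 counts consecutive "visits) that participants show at least 2 point reduction from baseline MG-ADL", and the opening sentence of SAP 4.3.4 also speaks of consecutive visits.
- SAP Table 1 has "Duration (average number of consecutive months) of meaningful improvement". Protocol Table 2 and Protocol 6.4.4 also use months.

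SAP Appendix 1, which records changes from the protocol, lists only the split of the primary analysis into imputation and ANCOVA. The endpoint is not in the testing order of SAP 4.3.7.

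**The concern.** The sentence that closes a run names the visit at which the reduction is absent. If that visit is the end point, the interval during which response was lost is counted as response. When the lapse falls at Week 24, the end point is Week 24 in either case, so the score cannot tell a participant who kept response from one who had just lost it.

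This endpoint serves the durability objective, and its mean in each arm will be reported in weeks. A score that credits the visit of loss is not the number of consecutive visits with response. Two competent programmers could also read the section differently and derive different data sets.

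**Working it through.** The plan gives no power, expected value or sample size for this endpoint, so there is no stated figure to reproduce. The check applies the rule to the visit grid.

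**Inputs.** Post-baseline visits are Weeks 2, 4, 8, 12, 16 and 20 (SAP 4.2.5) plus Week 24. The start, end, single-visit and rescue rules are those of SAP 4.3.4.

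**Three scores for the first run:**

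- Literal SAP rule: week of first visit without response (or 24 if never lost) minus week of first response; 1 if only one visit responds.
- Last-responding-visit rule: week of last responding visit in the unbroken run minus week of first response; 1 if only one visit responds.
- Protocol 6.4.7: number of consecutive responding visits.

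**Kept through Week 24 v first lost at Week 24:**

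| First response | Literal SAP (weeks) | Last responding visit (weeks) | Visit count |
|---|---|---|---|
| Week 2 | 22 v 22 | 22 v 18 | 7 v 6 |
| Week 4 | 20 v 20 | 20 v 16 | 6 v 5 |
| Week 8 | 16 v 16 | 16 v 12 | 5 v 4 |
| Week 12 | 12 v 12 | 12 v 8 | 4 v 3 |
| Week 16 | 8 v 8 | 8 v 4 | 3 v 2 |
| Week 20 | 4 v 1 | 4 v 1 | 2 v 1 |

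The literal rule ties in five of the six rows. Only the single-visit rule separates the Week 20 row.

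**Size of the credit.** After two responding visits the earliest possible lapse is Week 8, and visits from Week 4 on are 4 weeks apart. The credit for a lapsed run of two or more visits is therefore always 4 weeks. Response at Weeks 8 and 12 only scores 16 − 8 = 8, against 12 − 8 = 4 to the last responding visit.

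**Fit with the single-visit rule.** If runs ended at the lapse visit, a one-visit run would already score 4 − 2 = 2 (Week 2) or 4 (Weeks 4 to 20). Only a first response at Week 24 would score 0. If runs ended at the last responding visit, every one-visit run would score 0 and need a substitute value. The 1-week rule therefore suits the second reading. Under the first, a one-visit run scores 1 and a two-visit lapsed run jumps to 6 (8 − 2) or 8.

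**Fit with the rescue rule.** Take response at Weeks 2 to 20. Rescue at Week 24 stops the count before that visit, giving 20 − 2 = 18 if the preceding visit is used. Loss of response at Week 24 without rescue gives 22.

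**Effect on the arm difference.** Relative to the last-responding-visit rule, the literal rule reduces the difference (satralizumab minus placebo) by 4 × (placebo share − satralizumab share of lapsed runs with two or more responding visits). These shares are not in the documents. For illustration: 10% v 5% gives 0.2 week, 20% v 10% gives 0.4, and 50% v 25% gives 1.0.

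The shares were also simulated from the plan's means (2.3 v 4.3) and SD (3.97; SAP 2.2), with the full effect reached by Week 8, several assumed between-visit correlation patterns and no rescue. About 3–6% of participants per arm tie. The arm difference shrinks by about 0.04–0.2 week (1–6%), which corresponds to a gap in shares of 0.04/4 = 1 to 0.2/4 = 5 percentage points.

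**The case against.** The strongest reply is that loss is seen only at visits, so its true time lies between the last responding visit and the lapse visit. Onset is likewise dated at first detection, which shortens every run. Dating both ends at detection is a coherent convention, and SAP 4.4.2.1 uses it for the time-to-event endpoints. If onset and loss are both placed at interval midpoints (an assumption), a lapsed run lasts about 3–4 weeks longer than the span from first to last responding visit. The literal rule adds 4 and ending at the last responding visit adds 0. Relative to sustained runs, the first over-credits lapsed runs by about 2 weeks and the second under-credits them by about 2.

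That stands. A reader might infer that the rule inflates durability against the truth, or tilts the comparison towards satralizumab. The documents support neither: true duration is not observed, and the comparison usually moves towards no difference.

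The reply also notes that the phrase about visits defining the start and end of reduction can mean the last responding visit. It can, and the single-visit rule fits that reading. But the preceding sentence names the visit without response, so the ambiguity makes the section internally inconsistent and does not clear it.

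Three further points are fair. SAP section 1 lets the SAP supersede the protocol for filings. The Week 24 MG-ADL responder endpoint separates kept from lost response directly. The by-visit analyses and SAP 4.4.1 also address persistence. None of these reconciles 4.3.4 with SAP Table 6, or explains why loss of response and rescue close a run differently.

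**Conclusion.** The point holds as a mismatch between the derivation and the variable the plan names. Read literally, SAP 4.3.4 adds 4 weeks to every lapsed run of two or more responding visits and ties loss at Week 24 with sustained response for first response at Weeks 2 to 16. It conflicts with Protocol 6.4.7, SAP Table 6, its own rescue rule and the evident purpose of its single-visit rule.

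The numerical effect is small. The tie and shrinkage ranges rest on correlations and a time course that the documents do not give; a different onset pattern would change the percentages. The direction is conservative when placebo participants lapse more often, which is likely under the plan's means but not guaranteed.

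A reader might also infer a threat to the confirmatory conclusions. There is none: the endpoint is outside the SAP 4.3.7 sequence and type I error control is unaffected. The section is still worth correcting while the data are blinded, because the present text permits two different data sets.

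**What to change.** In SAP 4.3.4, define the end of the run as the last visit of the unbroken run with a reduction of at least 2 points and no rescue, and score that visit's week minus the first responding visit's week. Alternatively, analyse the protocol's count of consecutive responding visits. Keep the single-visit rule if weeks are used. Use one unit in Table 1, Table 6 and 4.3.4, and list any departure from the protocol's visit count in Appendix 1.

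The cost is one sentence, a line of derivation code and label edits, with no new data. The downside is that the last responding visit is a lower bound on the time of loss, so mean durations will be slightly shorter. The count to the lapse visit can be reported as a sensitivity analysis, which would show both bounds.
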